**MDS Cohort:**

7. Age  $\geq$  18 years at the time of signing the informed consent form.
8. Central confirmation of diagnosis of previously untreated primary or secondary MDS as per WHO classification ([Appendix B](#)). Results of central pathology review are required prior to receiving the first dose of IP.
9. Central confirmation of the categorization of the MDS risk classification, as per the IPSS-R Intermediate risk with  $>10\%$  blasts or poor or very poor cytogenetics, or IPSS-R High or Very High risk ([Appendix H](#)) (Results of central pathology review required prior to receiving the first dose of IP).

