4. INVESTIGATIONAL PLAN

4.1. Overall Study Design and Plan

This is a Phase 2, multicenter, randomized, parallel-group, open-label study evaluating the efficacy and safety of subcutaneous azacitidine either alone or in combination with durvalumab in two separate cohorts. Cohort 1 comprises subjects with previously untreated myelodysplastic syndrome (MDS) Revised International Prognostic Scoring System (IPSS-R) intermediate risk (in combination with more than 10% bone marrow (BM) blasts or poor or very poor IPSS-R cytogenetic risk), or IPSS-R high or IPSS-R very high risk, who are not eligible for HSCT. Cohort 2 comprises subjects with previously untreated acute myeloid leukemia (AML) (de novo AML with $\geq 20\%$ blasts) or secondary AML, as per WHO classification, who are elderly (≥ 65 years) and not eligible for HSCT, with intermediate or poor cytogenetic risk.

Subjects will be randomized (1:1 ratio) to receive one of the two treatment arms:

- Arm A (subcutaneous azacitidine plus durvalumab)
- Arm B (subcutaneous azacitidine alone)

[figure not shown]
The randomization process will aim to balance prognostic factors between study arms. For both cohorts (MDS and AML), subjects will be randomized and stratified according to their cytogenetic risk:

- Intermediate versus poor for AML ([Appendix 17.5](#)),
- Very good, good and intermediate versus poor and very poor for MDS ([Appendix 17.4](#)).

The randomized study will be conducted in 2 stages, with an interim analysis for futility purpose for each of the 2 disease cohorts determining whether that cohort proceeds to Stage 2. The interim analysis will be conducted in the MDS cohort when the first 30 subjects have completed 6 cycles of treatment unless they have established an earlier response (CR, mCR, PR or HI) or discontinued due to death or disease progression while the interim analysis in the AML cohort will be conducted when the first 50 subjects have completed 6 cycles of treatment unless they have established an earlier response (CR or CRi) or discontinued due to death or disease progression. Subjects assigned to Arm A, who received less than 3 cycles of durvalumab and continued under azacitidine monotherapy are to be excluded from the interim analysis.

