The End of Trial is defined as either the date of the last subject last visit for the completion of post-treatment follow-up, or the date of receipt of the last data point from the last subject that is required for primary, secondary and/or exploratory analyses, whichever is the later date. See Section 3.3 of the protocol.

Study Treatments

Subjects will be randomized 1:1 to receive either:

Treatment Arm A: Subcutaneous azacitidine (75 mg/m² daily for 7 days every 4 weeks [Q4W]) in combination with intravenous (IV) durvalumab at a dose of 1500 mg on Day 1 Q4W,

Or

Treatment Arm B: Subcutaneous azacitidine alone at the dose of 75 mg/m² daily for 7 days Q4W.

Table 2: Study Endpoints

Endpoint	Name	Description
MDS Cohort		
Primary	Overall response rate	Proportion of MDS subjects achieving an overall response (CR, mCR, PR or HI), based on IWG 2006 response criteria (Appendix 17.2).
Secondary	Time to response	Time from randomization to first documented response according to IWG 2006 response criteria (Appendix 17.2).
	Relapse-free survival	Time from the date CR or PR is first documented until the date of documented relapse, death from any cause, or lost to follow-up, whichever occurs first according to IWG 2006 response criteria (Appendix 17.2).
	Cytogenetic response (CyCR)	Proportion of subjects achieving complete cytogenetic response or partial cytogenetic response according to IWG 2006 response criteria (Appendix 17.2).
	Progression-free survival (PFS)	Time from randomization to the first documented PD, relapse or death due to any cause, whichever occurs first.
	Duration of response	Duration of response is defined as the time from first response observed (CR, mCR, PR or HI) until relapse, PD or death as defined by the IWG 2006 criteria (Appendix 17.2).
	Time to AML transformation	Time from randomization to AML transformation defined by at least 30% of myeloblasts either in the bone marrow or the peripheral blood.
	Transformation to AML	Proportion of subjects with disease transformation to AML.
AML Cohort		
Primary	Overall response rate	Proportion of AML subjects achieving an overall response (CR or CRi) based on modified IWG 2003 response criteria for AML. (Appendix 17.3).
Secondary	Time to response	Time from randomization to first documented response based on modified IWG 2003 response criteria for AML (Appendix 17.3).

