4.3.1. MDS Cohort

Sekeres et al ([Sekeres, 2014](#)) demonstrated that treating subjects with higher-risk MDS resulted in an overall response rate (ORR) (complete remission [CR], marrow complete remission [mCR], partial remission [PR], hematological improvement [HI]) of 36% after four cycles of azacitidine alone. This number is consistent with the “HI and better” rate from the AZA-MDS-001 trial of 36.4%.

Assuming a treatment effect of 100% relative improvement of ORR (from 36% to 72% ORR), a sample size of 72 subjects will provide a power of 90% to detect such an effect at the 5% level of statistical significance.

An interim analysis for futility purpose will be conducted on the first 30 subjects who have completed 6 cycles of treatment unless they have established an earlier response (CR, mCR, PR or HI) or discontinued due to death or disease progression. Subjects assigned to Arm A, who received less than 3 cycles of durvalumab and continued under azacitidine monotherapy are to be excluded from the interim analysis.

The MDS cohort will continue to enroll a total of 72 MDS subjects if one of the below conditions is met at the interim analysis:

- If the ORR (considering the composite score of CR + PR + mCR + HI) in the combination arm is numerically higher than or equal to the control group (azacitidine alone) or,
- If the response rate of one of the components of this composite score (in particular CR rate) in the combination arm is numerically higher than or equal to the control group (azacitidine alone) or,
- If evidence of a clinically meaningful difference in favor of the combination arm in a secondary endpoint (eg, duration of response) is provided.

If none of these conditions is met, then the cohort might be terminated. The data monitoring committee (DMC) will review the data at the time of interim analysis and will provide recommendation/advice to Celgene.

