10.1. Primary Efficacy Endpoint

The primary efficacy endpoint is the ORR and will be programmatically derived using the results/assessments generated by the central morphologic/cytogenetic and hematology laboratories. In case no central hematology results are available within +/- 8 days of bone marrow samples, local hematology results might be used if available. This analysis will be conducted after completion of the Stage 1 and Stage 2 portions of the study. A subject is considered evaluable for response if they have undergone at least one disease status assessment following treatment Cycle 6. Subjects who discontinue from the treatment phase before the first post baseline efficacy assessment (following treatment Cycle 3) will be replaced unless the subject had a documented progression of their disease or died and will be considered as non-responders. If one post baseline disease assessment is performed, this assessment would be considered for response.

The difference of the proportions for overall response between the azacitidine alone and combination therapy arms will be tested using a standard Wald asymptotic two-sided test with unpooled estimate of variance and presented along with corresponding two-sided 95% CIs.

The hypothesis tested will be:

$$H_0: d = 0$$

versus

$$H_a: d \neq 0,$$

Where $d = p_1 - p_2$ is difference in overall response rate in the combination therapy arm (p_1) versus the overall response rate in the monotherapy arm (p_2).

The test statistic is

$$z = \hat{d}/se(\hat{d})$$

Where, the standard error is computed from the sample proportions as

$$se(\hat{d}) = \sqrt{\frac{\hat{p}_1(1 - \hat{p}_1)}{n_1} + \frac{\hat{p}_2(1 - \hat{p}_2)}{n_2}}$$

Where \hat{p}_1 (respectively \hat{p}_2) is the estimated response rate in the combination therapy arm (respectively monotherapy arm) and is derived as the observed response rates in respective arms.

Myelodysplastic Syndromes Cohort

For the MDS cohort, the primary efficacy endpoint is the proportion of subjects achieving an overall response rate (defined as CR, PR, mCR, and/or HI) as determined using the International Working Group (IWG) 2006 response criteria for MDS ([Appendix 17.2](#)). The ORR will be summarized together with two-sided 95% CI. Subjects discontinued before 6-cycle treatment without achieving overall response will be counted as nonresponders.

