17.2. International Working Group (IWG) Response Criteria in Myelodysplasia (Cheson, 2006)

Altering Disease Natural History	
Complete remission (CR)	
 ▪ BM Blasts \leq 5% 
AND
 
 ▪ All of the following peripheral blood values met: 
 ▪ Hemoglobin \geq 11 g/dL ▪ Platelets \geq 100 x10⁹/L ▪ ANC \geq 1.0 x10⁹/L ▪ Peripheral Blasts=0% 
Labs must meet criterion for at least 28 consecutive days. If not confirmed for 28 days then response should be mCR.
 
In addition
 
 ▪ The 7/3 rule should be applied to Hemoglobin. ▪ Platelets collected 3 days period following Platelet transfusion will not be used - ANC values that must be at least 14 days following a G-CSF application
Partial remission (PR)	
 ▪ BM Blasts decreased by \geq 50% over pretreatment but still $>$ 5% 
AND
 
 ▪ All of the following peripheral blood values met: 
 ▪ Hemoglobin \geq 11 g/dL ▪ Platelets \geq 100 x10⁹/L ▪ ANC \geq 1.0 x10⁹/L ▪ Peripheral Blasts=0% 
Labs Must meet criterion for at least 28 consecutive days.
 
In addition
 
 ▪ The 7/3 rule should be applied to Hemoglobin. ▪ Platelets collected 3 days period following Platelet transfusion will not be used 
ANC values that must be at least 14 days following a G-CSF application

Marrow CR	
 ▪ Bone marrow: $\leq 5\%$ myeloblasts and decrease by $\geq 50\%$ over pretreatment with baseline BM blast $>5\%$ 
AND
 
 ▪ Not all of the following peripheral blood values met or none are met: 
 ▪ Hemoglobin ≥ 11 g/dL ▪ Platelets $\geq 100 \times 10^9/L$ ▪ ANC $\geq 1.0 \times 10^9/L$ ▪ Peripheral Blasts=0% 
Peripheral blood: if HI responses, they will be noted in addition to marrow CR

Stable disease (SD)	Any evaluable time point where criteria for all other response categories (i.e., CR, PR, PD, Failure due to death, Not Assessable) are not met
Failure	Death during treatment

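### The SAP reclassifies an unconfirmed CR as mCR without the mCR marrow conditions, so some MDS subjects count as primary responders although they meet no response definition

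*SAP*

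**What the plan says.** SAP 4.1 (Table 2) defines the MDS primary endpoint as "Proportion of MDS subjects achieving an overall response (CR, mCR, PR or HI), based on IWG 2006 response criteria". SAP 10.1 has it derived by program from central laboratory results, so the wording of the criteria table decides who is a responder.

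In SAP 17.2 the CR row requires marrow blasts of 5% or less and four peripheral blood limits (hemoglobin, platelets, ANC, no blasts) held for 28 consecutive days. It then says: "If not confirmed for 28 days then response should be mCR".

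The Marrow CR row of the same table requires blasts of 5% or less and a fall of at least 50% "over pretreatment with baseline BM blast" above 5%. It also requires that the four blood limits are not all met.

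Protocol Appendix D requires blasts of 5% or less and a fall of at least 50% for marrow CR. It has no fallback from CR to marrow CR. SAP section 15 says the response derivations were updated for consistency with the IWG criteria and does not mention the fallback.

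Subjects with low blasts can enter. Inclusion criterion 9 admits Intermediate-risk subjects with more than 10% "blasts or poor or very poor cytogenetics, or IPSS-R High or Very High risk". Only the first of these routes sets a blast minimum.

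**The concern.** The fallback and the Marrow CR row give different answers for the same subject, and the programmer must choose between them. Read literally, the fallback creates mCR responders whose marrow never met the mCR definition in either document. If such a subject also lacks HI, the subject enters the primary response rate only because counts were briefly within limits. The same label feeds the mCR component rate, best overall response, time to response and duration of response. In a cohort of 72, a few subjects matter.

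**Working it through.** **1. The rules applied to example subjects.** Each meets all four blood limits, but for fewer than 28 days.

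| Blasts, baseline to on-study | Fall | CR row with fallback | SAP mCR marrow conditions | Appendix D marrow CR |
|---|---|---|---|---|
| 3% to 3% | 0% | mCR | fails baseline and fall | fails |
| 7% to 4% | 3/7 = 43% | mCR | fails fall | fails |
| 6% to 5% | 1/6 = 17% | mCR | fails fall | fails |
| 15% to 3% | 12/15 = 80% | mCR | met | met |

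The first three are the problem. The fourth is a true marrow responder, but the SAP Marrow CR row read literally rejects this subject too, because all four blood limits are met. The fix has to keep this case.

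**2. Does HI capture the first three anyway?** Only sometimes. HI in SAP 17.2 needs an abnormal pretreatment value and improvement over at least 8 weeks. A subject with sustained HI whose counts reach CR level only briefly is already a responder. For that subject the fallback changes the mCR rate and best response, not the primary rate. The primary rate gains the subjects without HI: those with short-lived count recovery, and those whose counts were adequate at entry.

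**3. Can such subjects enter?** I scored every combination of the IPSS-R components (SAP 17.4) against inclusion criterion 9. Eligible profiles with blasts below 5%, out of 18 count combinations per cell:

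| Cytogenetics | 2% or less | Above 2% and below 5% |
|---|---|---|
| Good | 0 | 1 |
| Intermediate | 1 | 8 |
| Poor | 17 | 18 |
| Very poor | 18 | 18 |

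The total is 81 of 230 eligible profiles. This shows that low-blast entry is possible. The profiles are unweighted score combinations, so 81/230 does not estimate a share of subjects.

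**4. The plan's sample size.** SAP 4.3.1 states "Assuming a treatment effect of 100% relative improvement of ORR (from 36% to 72% ORR") and that "a sample size of 72 subjects will provide a power of 90% to detect such an effect at the 5% level of statistical significance". Allocation: "Subjects will be randomized (1:1 ratio) to receive one of the two treatment arms" (SAP 4.1). Test: the difference "will be tested using a standard Wald asymptotic two-sided test with unpooled estimate of variance" (SAP 10.1).

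n per arm = [p1(1−p1) + p2(1−p2)] × (z0.975 + z0.90)² / d² = (0.2304 + 0.2016) × 10.507 / 0.1296 = 35.02, rounded up to 36. The total is 72, as stated.

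Power at 36 per arm: 0.36 / √(0.432/36) = 3.286; 3.286 − 1.960 = 1.326; power 90.8%.

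**5. Size of the effect.** One subject is 1/36 = 2.8 points in an arm. With 13/36 responders on control, 21/36 on the combination gives z = 1.94 and 22/36 gives z = 2.19, so a single reclassified subject can decide a borderline result.

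For a wider view, assume a fraction f of true non-responders in both arms is counted through the fallback. Control becomes 0.36 + 0.64f and combination 0.72 + 0.28f.

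| f (assumed) | Control | Combination | Power, 36 per arm |
|---|---|---|---|
| 0 | 36.0% | 72.0% | 90.8% |
| 2% | 37.3% | 72.6% | 89.6% |
| 5% | 39.2% | 73.4% | 87.6% |
| 10% | 42.4% | 74.8% | 84.0% |
| 15% | 45.6% | 76.2% | 80.0% |

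**The case against.** The fallback has a sound purpose. Without it, the subject going from 15% to 3% with brief full count recovery would be neither CR nor, read literally, mCR. A sensible programmer might take it to mean that the mCR conditions are then checked. That purpose stands, but the sentence assigns mCR outright. Nor can the intent be to apply the whole Marrow CR row, because its blood condition rejects the subjects the fallback is meant to keep.

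The protocol's CR row prints no 28-day requirement, so some of these subjects would be CR under Appendix D if marrow maturation were normal. That is fair. But the SAP made duration part of CR. A subject who fails it needs another category, and both documents' mCR definitions require a fall of at least 50%. The baseline limit of 5% is the SAP's own addition, so the conflict with Appendix D concerns the fall only.

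Response without marrow change is already allowed through HI. This is correct and limits the effect to subjects without HI.

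A reader might infer that the fallback has no marrow condition at all. It sits in the CR row, so blasts of 5% or less still apply; a subject who enters at or below 5% has already met that.

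A reader might also infer that the SAP is wrong to define CR without a baseline condition. Appendix D's CR row has none either, so this is not an SAP error. Few subjects could meet CR at entry: only 3 of the 81 low-blast profiles carry no count points. Even those do not establish CR-level counts, since zero points needs hemoglobin of 10 g/dL and ANC of 0.8, against 11 and 1.0 for CR. The low-blast MDS categories in Appendix B also require anemia or a cytopenia.

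**Conclusion.** Wrong as written. SAP 17.2 assigns mCR to subjects whom its own Marrow CR row excludes, and to subjects without the fall in blasts that Appendix D requires. Those without HI become primary responders. The conclusion rests on the text alone.

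The size does not. The documents give no number affected; what follows from them is 2.8 points per subject per arm. The power figures assume equal misclassification in both arms, and the loss is modest at small shares. A reader might infer that the rule necessarily dilutes the treatment difference. The documents do not support that: brief count recovery could be more common in either arm, and the bias would then follow that arm. At the interim one subject is about 6.7 points (1/15, if 30 split evenly), but this carries little weight because the futility rule is non-binding and any one of three conditions allows the cohort to continue.

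**What to change.** Replace the fallback sentence in the CR row of SAP 17.2 with: if the counts are not confirmed for 28 days, classify as mCR only when baseline marrow blasts were above 5% and fell by at least 50% from pretreatment, without applying the mCR blood-value condition; otherwise assess for HI, and failing that SD. List the rule in SAP section 15.

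Do not refer the fallback to the whole Marrow CR row. Its blood condition would turn the subject going from 15% to 3% into SD unless HI lasted 8 weeks.

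Leave the CR definition aligned with the protocol. At most, add a sensitivity response rate that excludes subjects who already met every CR criterion at baseline.

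The cost is one wording change and one derivation change. The sample size stays at 72. The observed response rate may be slightly lower in both arms.

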Duration of response will be calculated only for subjects who achieve CR, mCR, PR or HI for the MDS Cohort, CR or CRi for the AML Cohort. Duration of response is defined as the time from first response observed until relapse, PD or death. Duration of response will be censored at the last response assessment date that the subject is known to be progression-free for:

- Subjects who have not relapsed, progressed or died at the time of analysis.
- Subjects who have withdrawn consent or are lost to follow-up prior to documentation of progression.

Censoring rules are defined in [Table 4](#).

Duration of response will be analyzed using the KM method. Median duration of response along with two-sided 95% CI will be provided for each cohort and treatment group.

In addition, the duration of each specific subcategory of response in the MDS Cohort (CR, mCR, PR or HI) and in the AML Cohort (CR) will be summarized using standard descriptive statistics.

Relapse-free Survival (RFS)

Relapse-free survival is defined only for subjects who achieve CR or PR for MDS subjects, CR and CRi for AML subjects, and is measured as the interval from the date of first documented response to the date of disease relapse or death from any cause, whichever occurs first. Subjects who are still alive and relapse-free will be censored at the date of their last response assessment. The RFS curve will be estimated using KM method.

Median RFS along with two-sided 95% CI will be provided for each cohort and treatment group. The RFS at 6 and 12 months will be estimated and compared using Kaplan-Meier (KM) method.

Censoring rules are defined in [Table 4](#).

Cytogenetic Response

External central pathology/cytogenetic reviewers will review the morphologic/cytogenetic data from bone marrow aspirate (BMA), bone marrow biopsies (if performed) to determine whether a subject achieved a cytogenetic response (complete or partial cytogenetic responses for MDS subjects and cytogenetic complete response for AML subjects). For cytogenetic response evaluable subjects (ie subjects with baseline cytogenetic abnormalities), the number and percentage of subjects who achieve the cytogenetic responses will be summarized together with associated two-sided 95% CI.

MDS Cohort:

Progression-free Survival (PFS)

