Progression-free survival is calculated as the time from randomization to the first documented progression, relapse or death due to any cause during or after the treatment period, whichever occurs first. Subjects who are still alive and progression-free will be censored at the date of their last response assessment. The PFS curve will be estimated using KM method.

Median PFS along with two-sided 95% CI will be provided for each cohort and treatment group. The PFS at 6 and 12 months will be estimated and compared using Kaplan-Meier (KM) method.

A sensitivity analysis of PFS will be performed, censoring PFS at the time of subsequent systemic anticancer therapy if the subject did not progress before that time.

Transformation to AML and Time to AML Transformation

Number of subjects with transformation to AML and time to transformation to AML will be summarized. Time to transformation to AML is defined as the time from the date of randomization until the date the subject has documented transformation to AML (at least 30% of BM blats). Subjects who do not transform to AML will be censored at the date last disease assessment date. Median time to transformation to AML and associated two-sided 95% CI will be estimated using KM method.

AML Cohort:

HI

Rate of HI – erythroid response (HI-E), hematological improvement – platelet response (HI-P) and hematological improvement – neutrophil response (HI-N) according to IWG 2006 response criteria for MDS ([Appendix 17.2](#)), will be provided together with Wald asymptotic two-sided 95% CIs.

Table 4: Event and Censoring Rules for Progression-free Survival, Duration of Response, Time-to-Response and Relapse-free Survival

Situation	Date of Progression or Censoring	Situation Outcome
Censoring Rules for PFS and DoR		
Progression	If the first PD is a scheduled assessment then Date of first PD; If the first PD is an unscheduled assessment and no previous assessment, then Date of PD; If the first PD is an unscheduled assessment and has previous assessment, then Date of previous assessment (regardless of the response type).	Event
Death between scheduled assessments or within the first two missed scheduled assessments	Date of death	Event
No progression	Date of last adequate assessment with evidence of no PD	Censored
Death or progression after two or more missed scheduled assessments	Date of last adequate assessment with evidence of no PD; if no adequate assessment exists then censored at date of first dose	Censored

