Disease Progression (PD)	
 ▪ If condition for Transformation to AML and relapse after CR/PR are not verified ▪ For patients with: 
 ▪ Nadir value less than 5% blasts: $\geq 50\%$ increase in blasts to $> 5\%$ blasts ▪ Nadir value 5% - 10% blasts: $\geq 50\%$ increase in blasts to $> 10\%$ blasts ▪ Nadir value 10% - 20% blasts: $\geq 50\%$ increase in blasts to $> 20\%$ blasts 
AND ANY OF THE FOLLOWING
 
 ▪ $\geq 50\%$ decrement from max level of ANC and ANC < 1.0 GI/L 
OR
 
 ▪ $\geq 50\%$ decrement from max level of Platelets and Platelets < 100 GI/L 
OR
 
 ▪ Reduction from max level of Hgb ≥ 20 g/L and Hgb < 110 g/L 
OR
 
 • Transfusion dependence (apply to baseline TI subjects only)

^a Dysplastic changes should consider the normal range of dysplastic changes (modification).

Source: Cheson BD, Greenberg PL, Bennett JM, Lowenberg B, Wijermans PW, Nimer SD, et al. Clinical application and proposal for modification of the International Working Group (IWG) response criteria in myelodysplasia. Blood. 2006; 108(2): 419-25.

Altering Disease Natural History	
Disease transformation	Transformation to AML (30% or more blasts)
Relapse after CR or PR	
 • BM % blast \geq baseline % blast and BM % blast \geq 5% 
OR
 
 • \geq 50% decrement from max level of ANC and ANC < 1.0 GI/L 
OR
 
 • \geq 50% decrement from max level of Platelets and Platelets < 100 GI/L 
OR
 
 • Reduction from max level of Hgb \geq 20 g/L and Hgb < 110 g/L 
OR
 
 • RBC/platelet transfusion is given after CR/PR

Cytogenetic Response	
Complete	Disappearance of the chromosomal abnormality without appearance of new ones
Partial	At least 50% reduction of the chromosomal abnormality

Hematological Improvement (HI)	

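### SAP response rules can mis-date secondary endpoints: MDS transformation and loss of HI are not listed PFS/DoR events, and AML progression lacks a stated reference value, floor, confirmation and precedence

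*SAP*

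**What the plan says.** **MDS progression.** SAP 17.2 opens the PD row with "If condition for Transformation to AML and relapse after CR/PR are not verified". It then requires a marrow rise from nadir joined by "AND ANY OF THE FOLLOWING" to a fall in counts or transfusion dependence. Transformation, at 30% or more blasts, is a separate category. The relapse row is limited to "Relapse after CR or PR".

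**MDS events.** SAP 10.2 defines PFS as "time from randomization to the first documented progression, relapse or death due to any cause during or after the treatment period". SAP Table 2 starts DoR at "first response observed (CR, mCR, PR or HI) until relapse, PD or death as defined by the IWG 2006 criteria", so HI responders are included. SAP Table 4 has no transformation row. Protocol Table 2 ends MDS DoR through Appendix D, which has a row for progression or relapse after HI. SAP 17.2 has no such row.

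**AML progression.** For a lowest marrow value up to 70%, SAP 17.3 calls PD at an increase of at least 50%. Protocol Appendix K requires more than 50% above baseline, persisting on two marrows at least one month apart. The DoR rule in SAP 10.2 reads "Duration of response is defined as the time from first response observed until relapse, PD or death". SAP 10.1 takes best overall response only before progression, and Table 4 censors TTR when the response follows PD.

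**Disclosure.** SAP Section 15 says the derivations were updated for consistency with the IWG criteria. It does not name these differences.

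**The concern.** Response is derived by program from central data, so the tables in SAP 17.2 and 17.3 are the operating rules. As written, MDS PFS and DoR can pass over a transformation, and MDS DoR can run on after HI has been lost. In AML, DoR can end while the marrow is still at CR/CRi level. A CR or CRi reached after an early SAP progression drops out of best overall response and is censored in TTR. The endpoints at stake are MDS PFS and DoR, and AML DoR, best overall response and TTR. Some of these dates would rest on programming choices that the SAP does not state.

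**Working it through.** The plan states no figure on this point, so there is none to reproduce. The check runs simple cases through the written rules.

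**1. MDS transformation, no prior CR/PR, nadir 15%.** The marrow criterion in SAP 17.2 for a nadir of 10% to 20% is a rise of at least 50% (1.5 × 15 = 22.5%) to above 20%. Both 29% and 30% meet it. The opening condition can be read in two ways: PD is barred if either transformation or relapse is met, or only if both are.

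| Marrow | Count or transfusion criterion met | Barred if either | Barred only if both |
|---|---|---|---|
| 29% | yes | PD | PD |
| 30% | yes | no event | PD |
| 29% | no | no event | no event |
| 30% | no | no event | no event |

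Nadirs of 4%, 8% and 19% give the same pattern on the first reading. With prior CR/PR, a marrow at 30% is at or above the MDS baseline value and meets the relapse row, so the gap is confined to subjects without CR/PR. Deleting the opening condition would not close it, because the last row stays without an event.

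**2. Loss of HI.** Hgb rises from 8.0 to 10.0 g/dL (HI-E needs at least 1.5) and falls back to 8.0, with the marrow steady at 12%.
- Appendix D, progression after HI: the fall is 10.0 − 8.0 = 2.0 g/dL against a limit of 1.5. Event.
- SAP PD: the Hgb criterion is met (fall of 20 g/L, value below 110 g/L). The marrow criterion needs at least 1.5 × 12 = 18% and above 20%. Not PD.
- SAP relapse: needs prior CR or PR. Not met.

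Result: DoR continues.

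**3. AML threshold, with the rise taken relative to the lowest value.** PD is met at 1.5 × nadir: 1% → 1.5%, 2% → 3%, 3% → 4.5%, 3.33% → 5%. For nadirs above 0% and below 3.33%, PD can be met while blasts are under the 5% CR/CRi limit. A CR/CRi subject has a nadir below 5%, so PD is met by 1.5 × 5 = 7.5% at the latest, half the marrow relapse limit of more than 15%.

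**4. AML path 40% (baseline), 10%, 15%, 4%.**
- SAP PD at the third marrow: 15 ≥ 1.5 × 10 = 15. Met.
- SAP PR at the same marrow: (40 − 15)/40 = 62.5% fall, still at least 5%. Met if platelets and ANC have recovered.
- Appendix K marrow criterion: above 1.5 × 40 = 60% on two marrows. Not met.

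The CR/CRi at 4% then follows SAP PD. Best overall response leaves it out and TTR is censored.

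**5. Counting noise, illustration only.** The assumptions are not in the documents: true blasts constant at 1%, 2% or 3%, 200 or 500 cells counted, binomial counts, first marrow below 5%. If PD is applied whenever met, the chance of PD within three later marrows is 49% to 75%. If CR/CRi takes precedence below 5%, it is 0% to 3% in five of the six settings and 20% in the sixth (200 cells, 3%).

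**The case against.** **AML reference value.** SAP 17.3 mentions the lowest or best value only in the condition that selects the rule. It does not say from what the 50% rise is measured. A reader might infer that 2% to 3% is definitely progression. The text does not go that far: measured from baseline, neither 2% to 3% nor the 40/10/15/4 path would be PD. The lowest value is the likeliest reference, because the condition is framed on it and the peripheral-blood rule names it. The rise is most naturally relative, because only the rule above 70% is marked as absolute.

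**Precedence.** A programmer may test CR/CRi before PD, which removes most of the sub-5% problem. That stands, but no visit-level order is written; the ranking in SAP 10.1 serves best response across visits. Such an order would also leave the 15% marrow in the 40/10/15/4 path untouched.

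**Transformation.** It is not lost altogether, as a reader might infer: it has its own proportion and time-to-event endpoints. They do not repair PFS or DoR. The reading that bars PD only if both conditions hold helps only when a count or transfusion criterion is also met.

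**Loss of HI.** Protocol 9.6.1.2 itself ends DoR at relapse or PD. The gap comes from dropping the Appendix D row through which Protocol Table 2 works, not from a changed DoR sentence.

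**Disclosure.** Footnote b marks AML PD as modified, but Appendix K carries the same flag, so it does not identify this change.

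**Conclusion.** The point holds for secondary endpoints and should be fixed. The MDS gaps follow from the text: transformation without prior CR/PR can go uncounted in PFS and DoR under either reading of the opening condition, and loss of HI alone does not end DoR. The AML departure from Appendix K on persistence is also plain. The 2% to 3% case and the 40/10/15/4 path rest on the lowest value being the reference, and the former also on CR/CRi not being tested first.

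The documents give no frequency for any of these cases. A reader might infer that the primary result is affected or that one arm is favoured. The documents support neither: the ORR definition carries no before-progression condition, and the rules are the same in both arms. The link to the futility decision is remote, because DoR is only an example in the third of three alternative conditions for continuing.

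**What to change.** These changes concern analysis definitions only, not treatment decisions.

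1. List transformation to AML as a PFS and DoR event in SAP Table 2, Section 10.2 and Table 4. First reconcile its definition: at the same 30% threshold, Table 2 counts marrow or peripheral blood, while Section 10.2 counts marrow only.
2. Restore the Appendix D event of progression or relapse after HI for DoR. State whether it applies only to HI-only responders or also to mCR with HI. Reconcile its 1.5 g/dL Hgb fall with the 20 g/L fall in the SAP relapse row.
3. State the reference value for AML PD and align the rule with Appendix K, or justify the departure. If aligned, say how PD is handled when there is no second marrow, since marrows are scheduled every third cycle. In either case, state that a visit meeting CR/CRi criteria is not PD, and which category applies when PR and PD are both met.
4. Reconcile the conjunction in the MDS PD row with the layout of Appendix D, which shows no such joining word, and name each departure in SAP Section 15.

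The cost is SAP wording and reprogramming on data already collected. MDS PFS and DoR may look slightly shorter, and AML DoR may look longer.
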